Appendix 2: Measuring participants' preferences and utilities

Background

Recurrent sore throats and tonsillitis are commonly experienced in childhood (98.7%), with the majority of children having more than 4 episodes of sore throats annually¹. There is currently no clear evidence on the best treatment option for recurrent sore throats and tonsillitis. Current treatments include pharmacotherapy or surgery. Parents of children who have undergone tonsillectomy tend to report a net improvement in children's condition, even though systematic reviews of the few clinical studies conducted so far do not show any significant clinical improvement in terms of severity and frequency of infections^{2;3}. The literature has highlighted that parental enthusiasm for tonsillectomy is dictated by their perceived improvement in healthrelated quality of life dimensions, such as behaviour, general wellbeing, growth and sleep⁴. Very little empirical data is available on preferences for health states related to sore throats and tonsillitis. Given the high prevalence, morbidity rates and conspicuous resource implications at both NHS and individual levels, the issue of improving insights into the sets of outcomes on which to base treatment decisions becomes of public health relevance. Investigators have highlighted the need to inform parents about the clinical effectiveness of tonsillectomy, and to obtain their informed values about the (perceived) benefits of the procedure weighted against its morbidity³. The measurement of parents' preferences for alternative non-surgical management and likelihood of adverse events is also important.

Objectives

- To establish the optimal treatment strategy from the perspective of parents in terms of their expected utility, and to determine to what extent this is preferred over its alternative;
- To ascertain whether and to what extent the (dis) benefits elicited from parents for tonsillitis is affected by the number of recurrent episodes (and their duration);
- To ascertain whether the parental decision making process is different from the one expressed by older children and, if yes, why and to what extent they are different;
- To provide insight into informed and shared medical choice models.

Methods

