The aim is to elicit utilities from the perspective of the parents, since they are the medical decision-makers for the child⁸. We assume that within a parental relationship, the 'principal-agent' model holds, i.e. the parents prefer the treatment which they believe to be in their child's best interest. Sensibly, we assume that children do not have a clear discernment between alternative treatments and outcomes, and therefore they will unavoidable rely on their parents' decisions. However, since older children (12+) are more mature and have more capabilities to make abstract thoughts and use complex language⁸, their utility values will also be elicited, and compared with those of the parents. This will allow us to test the agency model against the alternative hypothesis that parents aim to maximise their own utility function, including, in addition to the arguments of the child's utility function, factors such as the impact of the disease on the use of their own time and emotional status⁹, or the satisfaction of their own deep psychological needs¹⁰.

Sample size and recruitment process

A sample of 100 parents and 100 older children from 2 of the otolaryngology departments (Newcastle and Glasgow) will be telephoned and asked whether they will be willing to take part in the utility study. Interviews will take place at a mutually convenient place and time after the agreed course of treatment.

Development of scenarios

Scenarios describe the relevant outcomes. The process of scenario building is informed by the type of events, duration/frequency of events. This information has been derived from a review of the literature. Scenarios are outlined below.

The interview process

An interviewer's handbook and response booklet (i.e. a response marking form) have been prepared and are enclosed together with a consent form and information sheet. Interviews will be initially pre-tested with IHS staff, therefore a pilot study will be conducted before the main study on 4 or 5 pairs of parents and children aged 12-16. Interviews from the pilot study will be checked to ensure quality and standardisation of the interview process. Interviews for the pilot and main study will not be taped.

Analysis strategy

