Data will be collected on the utility scores of two health states estimated using standard gamble. Basic demographic data will be also be collected. Frequencies of the structure of the sample such as the male/female ratio and parent/own value ratio will be produced along with frequencies of the characteristics of the respondents such as stage of illness and socio economic status. The mean age of the sample will also be estimated. The mean utility values for each of the health states estimated using standard gamble will be calculated for the whole of the sample.

References

- 3. Marshall T. A review of tonsillectomy for recurrent throat infection. *Br J Gen Pract* 1998; **48:** pp 1331-1335.
- 4. Wolfensberger M, Haury J-A, Linder T. Patient satisfaction 1 year after adenotonsillectomy of their children. *Int J Pediatr Otorhinolaryhgol* 2000; **56**:pp 199-205.
- 6. Von Neumann, J. and Morgenstern, O. Theory of games and economic behaviour. 1944. Princeton University Press, Princeton, NJ.
- 7. Gafni, A and Birch, S. Preferences for outcomes in economic evaluation: An economic approach to addressing economic problems. *Social Science Med*_1995;**40**:767-776.
- 8. Stewart MG. Paediatric outcomes research: development of an outcomes instrument for tonsil and adenoid disease. *Laryngoscope* 2000; **Suppl.94**: pp 12-15.

NESSTAC Scenarios for utility study [for parents]

Health state X

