Your child gets 6-7 sore throats each year. These last 7 to 10 days each.

During this time your child...

- finds it hurts to swallow
- has a temperature, headache, earache
- feels sick and eats less.
- takes antibiotics and pain killers which may give them diarrhoea and a skin rash. After the first 5 days these symptoms begin to improve.
- has time off school, when they go back they are behind with the work.
- cannot take part in family, group or sporting activities.
- feels ill and is tired and irritable and may argue with you and your family.
- You are worried about them and may not be able to go to work or carry out your normal activities.

Health State Z

For up to 2 weeks after the treatment your child...

- Has a sore throat
- Feels sick
- Has a temperature
- Tired and irritable
- Small risk (1 in 20) that the tonsils will bleed and they have to have a blood transfusion
- Cannot go to school
- Cannot take part in family, group or sporting activities
- May wake up in the night
- You are worried and have to stay off work to look after them

After the first 2 weeks your child....

- Has 1-2 sore throats each year. These last 2-3 days each
- Has 2-3 days off school each year when they have a sore throat
- Feels ill and is tired and irritable when they have a sore throat
- You may have to take time off work when they have a sore throat
- When they do not have a sore throat your child has no pain or discomfort, behaves normally and can take part in their normal activities.

Good health

Your child...

has no pain or discomfort and is full of energy.

- behaves normally at home and school.
- can go to school and join in classes
- is able to join in family, group or sporting activities.
- You have no worries about their health. You are able to carry out your normal activities.

NESSTAC Scenarios for utility study [for 12-15 year olds]

Health state X

• You get 6-7 sore throats each year. These last 7-10 days each.

During this time...

- It hurts to swallow
- You have a temperature
- Headache
- Feel sick and eat less
- Take antibiotics which can give you diarrhoea and a rash
- You feel tired and irritable
- Cannot go to school
- Cannot do your usual activities
- Your parents are worried about you and may not be able to go to work.

Health State Z

For up to 2 weeks after the treatment you ...

- Have a sore throat
- Feel sick
- Have a temperature
- Feel tired and bad-tempered

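### Parent and child cards for health state X and Good health differ in content, so the promised parent-child utility comparison mixes respondent with description

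*Protocol*

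**What the plan says.** Appendix 2 of the Protocol gives four objectives for the utility substudy. One is "To ascertain whether the parental decision making process is different from the one expressed by older children", and, if so, why and by how much. Its Study sample section sets the perspective: "The aim is to elicit utilities from the perspective of the parents". For children of 12 and over it adds that "their utility values will also be elicited, and compared with those of the parents", and gives the purpose: "This will allow us to test the agency model against the alternative hypothesis that parents aim to maximise their own utility function". The recruitment target is "A sample of 100 parents and 100 older children from 2 of the otolaryngology departments".

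The scenario cards are printed at the end of Appendix 2, one set for parents and one for 12-15 year olds. In health state X the parent card says "After the first 5 days these symptoms begin to improve"; the child card has no such line. On treatment, the child card has only "Take antibiotics which can give you diarrhoea and a rash", where the parent card also names pain killers.

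The Analysis strategy section plans frequencies of sample characteristics, including the mix of parent and own-value respondents, and the mean age. Its one utility estimate is this: "The mean utility values for each of the health states estimated using standard gamble will be calculated for the whole of the sample".

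**The concern.** A standard gamble value belongs to the state as described and to the anchors against which it is gambled. If parents and children read different descriptions, a difference between their values may come from who is answering, from what was described, or from both. Every parent gets one text and every child the other, so no analysis of the resulting data can separate the two.

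What is at stake is the objective on parental against older children's decision making, and with it the test of the agency model. Two of the parent-only items, family arguments and absence of worry, bear on the parent's own emotional state. That is one of the factors the alternative hypothesis names, so the mismatch touches the very thing under test.

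A separate weakness is that the single utility estimate in the Analysis strategy averages over both respondent types. It is neither the comparison that the Study sample section promises nor a value from the parents' perspective.

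**Working it through.** **1. Health state X, side by side (Appendix 2, scenarios).** The number and length of episodes are the same in both versions: 6-7 a year, 7 to 10 days each.

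| Item | Parent card | Child card |
|---|---|---|
| Earache | yes | no |
| Pain killers | yes | no |
| Improvement after 5 days | yes | no |
| School | absence, then behind on return | cannot attend |
| Mood | tired, irritable, may argue with family | tired, irritable |

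These are differences of content, not of person or reading level. They do not all point one way. The improvement line makes the parent version milder; earache, arguments and falling behind make it worse. The sign of the net effect cannot be read from the text.

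**2. Good health.** Both versions cover pain, energy, behaviour, school and activities. The parent card adds that the parent is free of worry about the child's health; the child card has no worry item and mentions only the parents' work and activities. In the description of the chance board, the preferred outcome of the gamble is full health. If the Good health card describes that outcome, as it appears to, the upper anchor also differs by respondent.

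**3. Health state Z.** The two versions are nearly the same. The child card has bad-tempered for irritable, and says the parents are more worried where the parent card says worried. Any distortion for Z therefore comes mainly through the anchor.

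**4. Size of the problem for the comparison (illustration).** The protocol gives no alpha, power, effect size or SD for the 100 and 100, so that figure cannot be reproduced. Assume 100 completed interviews per group, treated as independent; two-sided alpha 0.05; utility SD σ from 0.15 to 0.30; and no true parent-child difference. If the wording alone shifts the mean by b, then

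SE = σ × √(2/100) = 0.1414σ, and

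P(significant) = Φ(b/SE − 1.96) + Φ(−b/SE − 1.96).

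Example: b = 0.05 and σ = 0.20 give SE = 0.0283 and b/SE = 1.77, so P = 0.42.

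| Wording effect b | σ = 0.15 | σ = 0.20 | σ = 0.25 | σ = 0.30 |
|---|---|---|---|---|
| 0 | 0.05 | 0.05 | 0.05 | 0.05 |
| 0.05 | 0.65 | 0.42 | 0.29 | 0.22 |
| 0.10 | 1.00 | 0.94 | 0.81 | 0.65 |

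For scale, the difference detectable with 80% power is (1.96 + 0.84) × 0.1414σ = 0.40σ, or 0.06 to 0.12 over the same SDs. A wording effect of that order would be as visible as a real difference in preference.

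**5. The whole-sample mean.** Pooled mean = (n_p × U_p + n_c × U_c)/(n_p + n_c), where p is parents and c is children. With assumed means of 0.90 for parents and 0.80 for children:

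- 100 + 100: (90 + 80)/200 = 0.85
- 100 + 60: (90 + 48)/160 = 0.86
- 100 + 30: (90 + 24)/130 = 0.88

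At equal numbers the pooled mean lies half the parent-child difference from the parents' mean. Otherwise it moves with the response mix. It equals the parents' mean only if the two groups agree.

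**The case against.** Three points can fairly be made for the plan.

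First, some adaptation for 12-15 year olds is proper, and the appendix itself calls standard gamble cognitively demanding. This justifies shorter sentences and a change from third to second person. It does not explain leaving out a symptom, a treatment and the course of the illness.

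Second, the Study sample section already promises a comparison, which needs values by group. The Analysis strategy records respondent type and does not rule out separate means, and further detail may sit in an analysis plan. This stands to a degree: pooling is one stated summary, not a decision never to separate the groups. But that summary does not serve the stated perspective, and separate reporting would not cure a confounding that is built into the cards.

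Third, state Z is nearly identical across versions. This stands. The comparison for Z is largely intact apart from the anchor, so the agency-model test is weakened but not worthless.

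A reader might also infer that the pooled mean goes into the cost-utility analysis and that its error can be stated in QALYs. The protocol does not support this. No section says the whole-sample mean is the input, and section 9.1.1.3 speaks of carers' preferences in that analysis. Moreover, a parent-child difference common to X and Z would cancel from the contrast between them, and any size for it would be assumed.

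**Conclusion.** The point holds for health state X and the Good health card. For X, and to a lesser degree for Z through the anchor, a parent-child difference in utility cannot be attributed to the respondent rather than to the text. This rests on comparing the printed cards and needs no numerical assumption. The direction is unknown.

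The size cannot be derived from the protocol. The false-positive probabilities of 0.22 to 0.65 for a wording effect of 0.05 depend on the assumed SDs, on that assumed effect, on independent groups and on 100 interviews completed in each. The 100 and 100 are people to be telephoned and asked, so completed numbers may be lower and unequal.

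The whole-sample mean is a lesser, related fault: as the only named utility estimate, it does not deliver the promised comparison or the stated perspective. It would be going too far to call it meaningless. It is a mix-weighted average of two groups. The matter deserves correction in a preference substudy; the primary clinical outcome is untouched.

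**What to change.** Before the pilot, align the parent and child versions of health state X and of Good health item by item. Each symptom, treatment, course and consequence should appear in both or in neither, with only person and age-appropriate wording changed. The small differences in state Z can be settled at the same time. Make matching edits to the interviewer's handbook and response booklet.

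In the Analysis strategy, replace the whole-sample mean with separate means for parents and for children for each state, and the parent-child difference with a confidence interval. Calculate the difference within pairs where both members were interviewed. Pairing also keeps the comparison to parents of 12-15 year olds, since parents of children from age 4 are eligible.

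The cost is a further amendment to Appendix 2, revision of materials that are already prepared, and probably a short re-test. Appendix 1 records changes to this substudy after pre-pilot work in November 2007, while Appendix 2 describes the pilot, with 4 or 5 pairs, as still to come. No extra interviews are needed. If interviews with the present cards have already taken place, the difference in content should be stated as a limitation of any parent-child result for state X.
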